## **Study Population**

The study will include all patients who are 18 years or older undergoing elective colectomy, whose data has been collected in the NSQIP® Procedure Targeted Colectomy dataset from 2014-2019, inclusively. The estimated sample size is approximately 130,000 patients.

We will exclude patients with American Society of Anesthesiologists (ASA) Physical Status (PS) V (defined as "5-Moribund") (ASA PS 6 - organ donation is not included within NSQIP). We will also exclude patients who are undergoing urgent or emergency surgery, or have indication for colectomy consisting of "Acute diverticulitis", "Enterocolitis (e.g. C. Difficile)", and "Volvulus" due to the non-elective nature of these pathologies. Patients with disseminated cancer, wound infection (i.e. potentially recent surgery), systemic sepsis, or ventilator-dependence preoperatively will also be excluded.

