## Model Prediction Endpoints

We will create a distinct time-to-event prediction model for each of the following new postoperative complications or adverse outcomes within 30 days postoperatively:

- Major medical complications: pneumonia, myocardial infarction (MI), cerebral vascular event (CVA), venous thromboembolism (VTE), acute renal failure (ARF), and sepsis or septic shock
- Adverse outcomes: mortality, readmission

The definitions of the complications, outcomes, and time-to-complication date criteria collected from NSQIP variables are included in Appendix 1 (Data Extraction Form).

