  - Cohort characteristics will be stratified by mortality, by each complication and by derivation vs. validation sets (please see list below). Continuous variables will be presented as mean (standard deviation) and median (IQR) for parametric and nonparametric data, respectively. Categorical variables will be

4

presented as frequency (%). For comparison amongst groups, ANOVA will be used for parametric data, Kruskal-Wallis for nonparametric data, and Chisquare tests for categorical data. Standardized mean difference will be presented. Exploratory visualizations will be performed.

- Distribution of time to complication data (time to any complication, and time to each complication): failure curves, i.e. plotting the 1-S(t) (survival function) to determine the risk of complication daily within 30 days
- Exploratory analysis for complications that tend to occur concurrently or are associated with each other
- 3. Model building
  - Models will be created using the entire dataset and using bootstrap validation
    - Individual models will be built for each outcome.
    - Assumptions for the Cox model will be checked prior to model building, including but not limited to:
      - 1. Proportionality: visual inspection of the Kaplan-Meier curves, Log Log S(t) test, Schoenfeld residuals. If these assumptions hold, we will use the Cox proportional hazards (CPH) modeling; if not, we will use the accelerated failure time (AFT) modeling.
      - 2. Competing risk: complications are assumed to be independent from each other. If mortality is >10%, it will be modeled as a competing risk (however, we do not anticipate mortality to be >10% for elective colectomy).
    - Sensitivity analyses
      - 1. After examining the temporal distributions of events, we may include complications that tend to happen earlier as predictors for complications that happen later, and may be related to earlier complications
      - 2. For the two models to predict time-to-event for adverse outcomes (mortality and readmission), we will perform sensitivity analysis to determine whether including the occurrence of major complications (pneumonia, myocardial infarction (MI), cerebral vascular event (CVA), venous thromboembolism (VTE), acute renal failure (ARF), and sepsis) as predictors improve discrimination and calibration
      - 3. Restricted cubic splines for continuous predictors (age, BMI, duration of surgery) to explore non-linear relationships

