      - 4. Compare cohort characteristics for patients with a complication or adverse event but missing time-to-event data, vs. patients without missing time-to-event data, to evaluate for the impact of bias from the exclusion of patients with missing time-toevent data
    - Additional analysis will be performed to improve time-to-event predictions, including but limited to:
      - 1. Accelerated failure time (AFT) modeling to directly model failure time. Compared to CPH, APT is more interpretable and robust with omitted predictor variables.
      - 2. Machine learning models that can facilitate time-to-event predictions: including but not limited to boosting trees, neural networks.
- 4. Model evaluation, with bootstrapped 95% confidence intervals and optimism

 Nov 9, 2021
 Protocol Version #2
 Ke et al.
 REB# H21-02670
 5

- AUROC, pseudo R-squared, scaled Brier, calibration plots
- 5. Sample size calculation
  - We used the PMSampsize package in R and followed guidance specifically for time-to-event multivariable modeling (6). Based on an event rate of 0.01 over 30 days (i.e. 0.00033333 per patient per day in the study period totalling 30 days), Cox-Snell R-squared 0.11 (the maximum for the event rate of 0.01 over 30 days) (6), 0.05 acceptable difference in apparent & adjusted R-squared, shrinkage 0.9, a minimum of 51 events (5091 patients, 15,2730 person-days of follow-up) are required for modeling with 30 predictor variables.

Data will be analyzed using R and/or Python.

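### The 51-event minimum enters R-squared at its ceiling; below about half of that ceiling, 5,091 patients miss the plan's own 0.9 shrinkage target

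*Combined protocol and SAP*

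**What the plan says.** Item 5 of the Statistical Analysis section (Sample size calculation) uses the pmsampsize package and published guidance for time-to-event prediction models. Its inputs are:

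- **Event rate:** "Based on an event rate of 0.01 over 30 days (i.e. 0.00033333 per patient per day in the study period totalling 30 days").
- **Anticipated R-squared:** "Cox-Snell R-squared 0.11 (the maximum for the event rate of 0.01 over 30 days").
- **Optimism limit:** "0.05 acceptable difference in apparent & adjusted R-squared".
- **Target shrinkage:** 0.9.

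The result is "a minimum of 51 events (5091 patients, 15,2730 person-days of follow-up) are required for modeling with 30 predictor variables". (The person-days figure has a misplaced comma and should read 152,730.)

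Three other statements bear on how this figure is used:

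- Model Prediction Endpoints: "We will create a distinct time-to-event prediction model for each of the following new postoperative complications or adverse outcomes". Six complications and two adverse outcomes are listed, so eight models.
- Study Population: "The estimated sample size is approximately 130,000 patients".
- Model building: "Models will be created using the entire dataset and using bootstrap validation".

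The documents give no expected R-squared below the maximum, no calculation at another value, and no event rate for any individual outcome.

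**The concern.** The R-squared in this method should be what the model is expected to achieve in the target population. The smaller it is, the weaker the signal and the more patients are needed to hold overfitting to a given level. Entering the theoretical maximum assumes a model that explains all the variation that can be explained, and it returns close to the smallest sample size the method can give: 51 events for 30 predictors, or 51/30 = 1.7 events per predictor.

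The figure is the plan's only stated threshold for whether there are enough events to fit a model. It is computed once, at a 1% rate, for eight outcomes whose rates may differ widely. Taken at face value, 51 events in 130,000 patients is a rate of 51/130,000 = 0.04%, so the stated minimum would pass even very rare outcomes as adequate for 30 predictors.

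**Working it through.** **Inputs from the plan.** Event rate p = 0.01 over 30 days; R-squared (R²) = 0.11; R-squared difference 0.05; shrinkage S = 0.9; P = 30; cohort about 130,000.

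**Formulas.**

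- Maximum Cox-Snell R² = 1 − exp[2(p ln p − p)].
- Shrinkage criterion: n = P / [(S − 1) ln(1 − R²/S)].
- R-squared-difference criterion: S₂ = R² / (R² + 0.05 × max R²), then the same formula for n with S₂ in place of S.

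**Step 1: reproduce the plan.**

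- Maximum R² at p = 0.01 is 0.106, which rounds to the stated 0.11.
- Shrinkage criterion with R² = 0.11, S = 0.9: n = 30 / [(−0.1) ln(1 − 0.11/0.9)] = 2,302.
- Difference criterion with R² and the maximum both 0.11: S₂ = 0.11 / 0.1155 = 0.952, giving n = 5,090.2, hence 5,091.
- 5,091 × 0.01 = 50.9, hence 51 events; 5,091 × 30 = 152,730 person-days.

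All stated figures reproduce. The 0.9 shrinkage target plays no part in the result: it asks for 2,302 patients, and the 5,091 comes wholly from the R-squared-difference criterion.

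**Step 2: break-even.** Setting the shrinkage criterion to n = 5,091 with S = 0.9 and P = 30 and solving for R² gives 0.0515. That is 49% of the unrounded maximum 0.106, or 47% of 0.11. As a guide to scale, if the linear predictor is normal in each outcome group, it corresponds to an AUROC of about 0.96.

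**Step 3: lower values of R².** These are assumed values, because the documents supply none. The rate is 1%, with 30 parameters and the unrounded maximum 0.106. The minimum for the first three rows is set by the shrinkage criterion.

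| Share of maximum | R² | Minimum patients | Minimum events | Ratio to 5,091 | Shrinkage at 5,091 | Shrinkage at 130,000 |
|---|---|---|---|---|---|---|
| 30% | 0.0318 | 8,336 | 84 | 1.6 | 0.85 | 0.993 |
| 15% | 0.0159 | 16,823 | 169 | 3.3 | 0.73 | 0.986 |
| 10% | 0.0106 | 25,310 | 254 | 5.0 | 0.64 | 0.979 |
| 50% | 0.0530 | 5,492 | 55 | 1.1 | 0.903 | 0.996 |

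At 50% the shrinkage criterion alone needs 4,941, so 5,091 still just meets 0.9; the 5,492 comes from the R-squared-difference criterion. With the plan's rounded maximum of 0.11, the 30%, 15% and 10% rows become 8,031, 16,214 and 24,396 patients.

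Expressed by AUROC under the same normal assumption: 0.80 gives R² = 0.0138, 19,452 patients and 195 events; 0.75 gives R² = 0.0089, 30,142 patients and 302 events. Expected shrinkage at 130,000 for AUROC 0.75 is 0.975.

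**Step 4: rarer outcomes in the full cohort.** With 30 parameters, 130,000 patients meet shrinkage 0.9 down to event rates of about 0.04% (R² at 30% of its maximum), 0.09% (15%) or 0.14% (10%). For an assumed 0.2% outcome there would be about 130,000 × 0.002 = 260 events. At AUROC 0.80, 192 are needed, which is met. At AUROC 0.75, 298 are needed, and expected shrinkage is 0.89, slightly short.

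**Step 5: parameter count.** What matters is the number of parameters, not of variables. The Candidate predictors section lists about 22 variables, one of which (indication) has six categories. The sensitivity analyses add "Restricted cubic splines for continuous predictors (age, BMI, duration of surgery) to explore non-linear relationships" and, for mortality and readmission, the six complications. If 30 is the base, four knots (assumed) on three variables add 6 terms, giving 36; the complications bring it to 42. At 15% of the maximum these need 202 events (20,188 patients) and 236 events (23,553 patients).

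**The case against.** The strongest answer is that nothing turns on 5,091. This is a fixed registry cohort of about 130,000, all of it used for modelling. The minimum is a feasibility floor, not a recruitment target or a subset size, and bootstrapped optimism will measure overfitting directly. That stands for outcomes near 1%, and it is why the point is a correction to the plan and not a threat to the main models. It does not rescue the figure: optimism estimated after fitting cannot justify a published minimum, nor settle beforehand how many parameters a rare outcome can support.

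Second, no documented outcome is shown to fall short. True: the plan gives no rates by outcome, and the one shortfall shown rests on two assumptions (0.2% and AUROC 0.75) and is marginal. But the plan's figure cannot tell such cases apart.

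Third, some of the figures are soft:

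- The ratio at 50% of maximum is partly rounding. Like for like, moving from 100% to 50% of 0.106 takes the minimum from 5,337 to 5,492, about 3%.
- The 36- and 42-parameter figures concern sensitivity models only, and 30 may already allow for multi-level predictors.
- The AUROC conversions treat the outcome as binary and are illustrations.
- The 15% value is as undocumented as any other, which is why a range is shown.

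These are fair limits. None of them touches the break-even at about half the ceiling.

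**Conclusion.** The concern holds. The stated minimum is correct arithmetic on an input that no document supports, and it does not deliver the plan's own 0.9 shrinkage for any R-squared below about 0.0515. Over an assumed range of 30% down to 10% of the maximum, the minimum at a 1% rate is 1.6 to 5.0 times the stated patient number. This rests on 30 parameters, a 1% 30-day rate and R-squared values chosen for illustration.

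The planned cohort is adequate at 1% in every scenario examined. What needs correcting is the published threshold and the absence of a check by outcome; only an outcome much rarer than 1% could be affected in practice. The correction should be made, but the main models are not endangered.

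**What to change.** Redo the calculation with a justified R-squared below the maximum and show a range. Possible wording, with 15% as a placeholder to be replaced by a justified value:

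> *Assuming a Cox-Snell R-squared of 0.016 (15% of the maximum 0.106 at a 1% 30-day event rate), 30 parameters and shrinkage 0.9, at least 169 events (16,823 patients) are required; the range is 84 to 254 events for 30% to 10% of the maximum. The planned cohort of about 130,000 meets this at a 1% event rate.*

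Add a short table repeating the calculation for each of the eight outcomes at its own event rate. Count every parameter, including category levels and, for the sensitivity models, spline terms and added complication predictors. State that where an outcome has too few events, its model will use fewer parameters or penalised fitting.

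The cost is one rewritten paragraph and one table, and a required figure that looks less favourable. No extra patients are needed, and outcomes near 1% need no change of analysis.

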# List of variables in cohort characteristics (Please see Appendix 1 for details)

# Preoperative and intraoperative variables:

- Age, sex, race, height, weight, body mass index (BMI)
- ASA, diabetes, smoker within one year preoperatively, severe obstructive chronic pulmonary disease (COPD), ascites, congestive heart failure (CHF), hypertension on medications, preoperative renal failure (acute renal failure, dialysis, and/or GFR <60 based on preoperative creatinine), preoperative functional status, dyspnea, coagulopathy
- Steroid/immunosuppressant use preoperatively
- Chemotherapy within 90 days preoperatively
- Primary indication for colectomy (categorized and full list)
- Surgical approach: minimally invasive vs. open (categorized and full list)
- Total operation time
- Use of regional anesthesia as an additional anesthetic technique (epidural, peripheral, spinal)
- Wound classification (end of surgery)

# **Postoperative variables:**

- Myocardial infarction
- Stroke/CVA
- VTE (composite: pulmonary embolism, DVT)
- Pneumonia
- Acute renal failure
- Sepsis or septic shock (composite of systemic sepsis and septic shock)
- Readmission: also present % unplanned
- Mortality
- Complication or death (composite of the major complications modeled)
- Time to first complication or death (composite of the major complications modeled)
- Wound issues (composite: superficial and deep infection, wound disruption)
- Non-home discharge
- Bleeding requiring transfusion
- Anastomotic leak
- Prolonged postoperative ileus (nothing by mouth or nasogastric tube)
- Urinary tract infection
- Transfusion (packed red blood cell (PRBC) within the first 72 hours of surgery start time)
- Cardiac Arrest Requiring cardiopulmonary resuscitation (CPR)

 Nov 9, 2021
 Protocol Version #2
 Ke et al.
 REB# H21-02670
 6

- On ventilator >48h postoperatively
- Still in Hospital > 30 Days
- Unplanned reoperation

